4.5. Safety and PK Variables

The following section describes the safety and PK endpoints. Endpoints related to Holter ECG time points are described separately in the ECG SAP ([Appendix 4](#)). For a detailed schedule of procedures refer to [Table 2](#). Refer to Section 3 for a list of the primary and secondary objectives and outcomes.

Incidence, relatedness, and severity of treatment-emergent AEs and SAEs will be recorded from time of dose to Final Visit, or ET Visit.

The following other safety parameters will be assessed for each dosing period and at the Final Visit or ET Visit:

- Change from baseline in clinical safety laboratory parameters, as measured at the In-Patient Follow-up visit (the day after dosing), after a minimum 4 h fast.
 - Chemistry: Sodium, Potassium, Magnesium, Chloride, Total Carbon Dioxide (CO₂), Glucose (Fasting), Blood Urea Nitrogen (BUN), Creatinine, Estimated Glomerular Filtration Rate (GFR), Total Protein, Albumin, Aspartate Aminotransferase (AST), Alanine Aminotransferase (ALT), Alkaline Phosphatase (AP), Total Bilirubin, and Direct Bilirubin
 - Hematology: Hemoglobin, Hematocrit, Erythrocytes, Leukocytes, Neutrophils (absolute count), Lymphocytes (absolute count), Monocytes (absolute count), Eosinophils (absolute count), Basophils (absolute count), and Platelets
 - Urinalysis: Glucose by Dipstick, Protein by Dipstick, Hemoglobin by Dipstick. If dipstick testing is abnormal, a complete urinalysis with microscopic evaluation will be performed. Urinalysis microscopic evaluation parameters that will be graded and summarized may include Erythrocytes by Microscopic Evaluation, Leukocytes by Microscopic Evaluation, and Bacteria by Microscopic Evaluation.
- Change from baseline in vital signs parameters, as measured at 1 h (±10 minutes), 2 h (±10 minutes), 4 h (±10 minutes), and 24 h (±2 h) after dosing.
 - Systolic Blood Pressure, Diastolic Blood Pressure, Heart Rate, Respiratory Rate, and Temperature
- Change from baseline in 12-lead standard ECG with 10-sec rhythm strip parameters, as measured 1 h (±10 minutes), 2 h (±10 minutes), 4 h (±10 minutes) and 24 h (±2 h) after dosing.

-
- Overall interpretation of standard 12-lead ECGs (normal, abnormal not clinically significant [NCS], or abnormal clinically significant [CS]), and the following parameters: PR Interval; QRS Duration, QT Interval; QTcF Interval, RR Interval, ECG Mean Ventricular Rate

Glomerular filtration rate, as estimated by the Cockcroft-Gault equation, will be entered directly into the clinical database.

AEs will be graded for severity and relationship to study product, as described in Section 9.2 of the protocol v3.0. Adverse and serious adverse events are defined in Section 9.2 of protocol. Vital signs and ECG results will be graded according to toxicity scales in [Table 3](#). Clinical laboratory results will be graded according to toxicity scales in [Table 4](#).

Blood (plasma) samples for PK analysis will be collected at the following time points for each dosing period: within 30 minutes before dosing, and at 0.5 h (± 5 minutes), 1 h (± 5 minutes), 2 h (± 5 minutes), 3 h (± 10 minutes), 4 h (± 10 minutes), 6 h (± 10 minutes), 8 h (± 15 minutes), 12 h (± 15 minutes), and 24 h (± 2 h) after dosing, or ET if it occurs within 24 h of dosing. Zoliflodacin concentrations will be measured from plasma samples by the bioanalytical laboratory.

5. SAMPLE SIZE CONSIDERATIONS

Enrollment of 72 subjects would provide at least 84% power to conclude a negative effect, given that up to 16 subjects may withdraw early prior to beginning to replace subjects (at least 56 subjects evaluable), and assuming a standard deviation (SD) of $\Delta\Delta\text{QTcF}$ of 7 msec and an underlying effect of 5 msec.

6. GENERAL STATISTICAL CONSIDERATIONS

6.1. General Principles

Safety, and PK will be summarized by treatment (see Section 3.3), with the order of treatments presented as: 1) 2 g zoliflodacin, 2) 4 g zoliflodacin, 3) placebo, and 4) 400 mg moxifloxacin. Summaries of frequencies and percentages will be presented for categorical data, and summary statistics including the mean, median, SD, minimum value (min), and maximum value (max) will be presented for continuous demographic and safety data. The method of Wilson will be used for CIs of proportions for safety data. The safety population will be used for summaries of demographics and safety endpoints.

Sort order of listings will be by parameter, followed by sequence, followed by subject ID, followed by date (or day) and time. If a listing will not follow this sort order, the sort order to be used can be found in Instruction text for the listing. The sort order of clinical laboratory, vital signs, and ECG parameters is described in Section 9.

6.2. Timing of Analyses

The final analysis will be performed after database lock. There are no planned interim analyses.

6.3. Analysis Populations

All analysis populations to be used in the final analysis are described below. Reasons for exclusion from each analysis population will be summarized by sequence in [Table 8](#) and listed ([Listing 4](#)). Although there may be multiple reasons for exclusion from the PK population, only one reason will be counted when summarizing reasons for exclusion from analysis populations in the table. The order that reasons will be considered are the same as the order shown in the table shell. For example, if a subject was excluded from the PK Population and had insufficient concentration data to compute any PK parameters, the subject would be counted for exclusion from the PK analysis subset for reason of exclusion from the PK population only, because that reason appears in the table before the reason of insufficient concentration data.

6.3.1. Safety Population

All subjects who received at least one dose of study drug (zoliflodacin, placebo, or moxifloxacin) will be included in the safety population and analyzed as treated.

6.3.2. PK Population and PK Analysis Subset

The PK analysis population will consist of all subjects who received zoliflodacin and have at least one quantifiable post-dosing drug concentration measured. The PK analysis subset will be based on the PK population, which includes all subjects who completed the PK part of the trial without any protocol violations that would likely affect the PK results and who have evaluable plasma concentration data for zoliflodacin from whom at least a subset of the designated PK parameters can be determined. If any subjects are found to be noncompliant with respect to dosing or have incomplete data, a decision to include them in the analysis will be made on a case-by-case basis.

6.3.3. Holter ECG Analysis Population

The Holter ECG Analysis Population will include all subjects who have received at least one dose of zoliflodacin, moxifloxacin or placebo, treatment, without protocol deviations potentially impacting the ECG intervals and have baseline ECGs and at least one post-dose ECG assessment.

6.3.4. Pharmacokinetic-ECG (PK-ECG) Analysis Population

PK-ECG Analysis Population will be a subset of the Holter ECG Analysis Population and will include all subjects in the Holter ECG Analysis Population with at least one plasma concentration value in the zoliflodacin treatment with a corresponding Holter ECG measurement value at the same nominal timepoint.

6.4. Covariates and Subgroups

The protocol does not define any formal subgroup analyses.

6.5. Missing Data

No imputation of missing data is planned.

6.6. Interim Analyses and Data Monitoring

No interim analysis is planned.

6.7. Multicenter Studies

This is a single site study.

6.8. Multiple Comparisons/Multiplicity

Safety and PK analyses will not adjust for multiple comparisons. For multiplicity in the ECG analysis, see the ECG SAP ([Appendix 4](#)).

7. STUDY SUBJECTS

7.1. Disposition of Subjects

Screened subjects who were ineligible for enrollment in the study (screen failures) or eligible but not enrolled will be summarized by inclusion and exclusion criteria ([Table 6](#)).

Subject disposition will be summarized by sequence ([Table 7](#)), showing the number of subjects by sequence who were screened, enrolled, dosed, completed sample collection, or completed follow up. Eligibility for each analysis population will be summarized by sequence ([Table 8](#)).

A flow diagram will summarize screening, enrollment, and disposition of subjects by sequence, including number of subjects dosed, number of subject completing ECG follow-up, and reasons for early termination or discontinuation of study product ([Figure 2](#)).

Subjects who terminated early from the study will be listed ([Listing 1](#)). Subjects who were excluded from an analysis population will be listed ([Listing 4](#)).

7.2. Protocol Deviations

A summary of protocol deviations will be presented by deviation category and deviation type ([Table 5](#)). This table will provide both the number of subjects and the number of deviations for each category. All subject-specific protocol deviations and non-subject-specific protocol deviations will be listed ([Listing 2](#) and [Listing 3](#)).

8. EFFICACY EVALUATION

Not Applicable. For analysis of Holter ECG endpoints, see the ECG SAP ([Appendix 4](#)).

9. SAFETY EVALUATION

All safety analyses will be presented using the safety population. Subjects will be grouped for summary statistics by Treatment, as defined in Section 3.3.

When calculating the incidence of AEs (i.e., on a per subject basis), each subject will be counted once and any repetitions of unsolicited AEs within a subject (by treatment) will be ignored for events coded in the same category by the Medical Dictionary for Regulatory Activities (MedDRA®). The denominators for percent values will be indicated within the table or table header and denominators will consist of the maximal size of the safety population in the indicated observation period. Moreover, events thus summarized will be coded to the highest severity observed. If the time interval defined by the start date and end date of the AE overlaps more than 1 period, the AE will be associated with treatment immediately preceding the AE start date only, and the AE will be graded according to the maximum severity of the event at any time prior to the AE end date. Abnormal laboratory values or clinical findings measured after dosing will be reported using the toxicity scales in [Table 3](#) and [Table 4](#).

All laboratory, vital signs, and ECG results obtained after the first dose that have programmable criteria described in the toxicity scales will be graded for the CSR according to the programmable criteria, and toxicity grades of mild, moderate, or severe will be indicated for the result in the listings. For criteria involving a change from baseline, the baseline to be used is described in Section 3.3.

If a subject was accepted into the trial with a laboratory, vital signs, or ECG parameter value that overlaps with values used for grading Grade 1 laboratory abnormalities, the result will only be graded (mild or worse) if the post-dose measurement of the parameter is different (worse) than baseline. In other words, a result will be graded as mild, moderate, or severe if and only if it both meets the grading criteria in [Table 3](#) or [Table 4](#) and is worse than baseline by any amount.

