- Review inclusion/exclusion criteria to confirm the subject remains eligible for enrollment
- Update MH (Day -1 in Period 1 only)
- Update Prior Medications
- Perform abbreviated PE (Perform on each check-in. In Period 1, do not perform only if the screening PE was completed ≤ 7 days from dosing.)
- Obtain VS
- Obtain weight
- Obtain blood and urine samples for clinical laboratory tests (collect on each check-in). In Period 1, do not collect if screening samples were collected ≤ 7 days from dosing.)
- For all women, a serum β -HCG pregnancy test will be done, and negative results confirmed before dosing
- Obtain urine sample for toxicology
- Perform urine alcohol test for alcohol use
- Obtain 12-lead standard ECG with 10-sec rhythm strip
- Counsel to avoid rigorous physical activity
- Review AEs/SAEs (Day -1 in Periods 2, 3, and 4, respectively, on study Days 8, 16, and 24)

Subjects who still meet the eligibility criteria on Day -1 before Period 1 will be admitted to the CTU on the same day.

For subsequent dosing periods (2, 3, and 4), subjects will be admitted on Day -1. Any new symptoms or abnormal assessments will be reviewed prior to dosing, and recorded as AEs.

Eligibility for continuation of dosing (dose 2, 3 and 4):

Dosing for subsequent periods may proceed if:

- A negative serum pregnancy test on Day -1 of each dosing period
- Females of childbearing potential and males still agree to use acceptable contraception for the duration of the trial and for 30 days (females) or 90 days (males) after Final Visit
- One of the following:
 - Subjects who did not experience any AE since the last dose administration
 - Any new or prior AEs were grade 1 or resolved, and in the opinion of the site principal investigator or appropriate sub-investigator, the AEs, individually or in cluster, do not pose a risk to the subject or would be likely to confound interpretation of the results.
 - Any new or prior AEs that were grade 2, should be either resolved or downgraded to Grade 1 and in the opinion of the site principal investigator or appropriate sub-investigator, the AEs, individually or in cluster do not pose a risk to the subject or would be likely to confound interpretation of the results.

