 - Any new or prior grade 3 AEs that were judged unrelated to study drug should be either resolved or downgraded to Grade 1 and in the opinion of the site principal investigator or appropriate sub-investigator, the AEs, individually or in cluster do not pose a risk to the subject or would be likely to confound interpretation of the results.

If a subject has a Grade 3 AE judged related to study drug administration, this subject will be withdrawn from the study and will not receive subsequent dosing. For all other AEs, dosing may be delayed up to 14 days in order to follow the AE for downgrading or resolution according to the above. If the subject does not meet the criteria for dosing specified above in 14 days, this subject will be withdrawn from the study and will not receive subsequent dosing.

After admission to the CTU, the subject will fast at least 8 h before dosing but will have access to water during that period.

7.4 Inpatient period (Days 1-2 in each dosing period) (Overall, Days 1-2, 9-10, 17-18, and 25-26 for dosing periods 1, 2, 3 and 4, respectively)

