- Measurements taken during the Final Visit will use the last measurement prior to the first dose as baseline for the analysis time points labeled “Final Visit” and will use the last measurement prior to the fourth dose as baseline for the analysis time points labeled “Follow-up”. Listings will show both of the two change from baseline values for Final Visit. The justification for including the Period 1 baseline for the Final Visit is to show overall changes (ideally absence of changes) over the course of the study. Grading of change from baseline will be based on the Period 1 baseline only.

Treatment Associated with Records

Treatment associated with post-dose records will always be the last type of treatment received before the (start) date or date-time associated with the record. AEs will be summarized by treatment and listings of all safety endpoints will include treatment, as it is defined here.

Possible values of treatment, in order of presentation in the CSR, are: 2 g zoliflodacin, 4 g zoliflodacin, placebo, and 400 mg moxifloxacin.

Study Day and Day in Period

Study Day and Day in Period will primarily be used in listings to refer to timing of assessments and events relative to first dosing (Study Day) or dose for the respective period (Day in Period).

The day that the first dose of study product is received is considered Study Day 1 for each subject. The day prior to first dose is considered Study Day = -1, not Study Day = 0.

The day that the dose of study product is received is considered Day in Period = 1 for each subject and each dosing period. The day prior to dosing for each period is considered Day in Period = -1, not Day in Period = 0.

Treatment Sequence

Each subject will receive one dose orally of each of four treatments, labeled A through D:

- Treatment A: zoliflodacin 2 g
- Treatment B: zoliflodacin 4 g
- Treatment C: placebo
- Treatment D: moxifloxacin 400 mg

Each subject will be randomly allocated to one of 12 dosing sequences before dosing on Day 1, Dosing Period 1, and receive a single dose of the preceding four study drugs on different days according to their randomly-assigned dosing sequences. The 12 dosing sequences, in order that they will be presented in the report, are ABCD, ACDB, ADBC, BADC, BDCA, BCAD, CDAB, CABD, CBDA, DCBA, DBAC, and DACB.

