9.3. Adverse Events

When calculating the incidence of AEs (i.e., on a per subject basis) within a given AE class (MedDRA category), each subject will only be counted once for each treatment and any repetitions of AEs within a subject/treatment will be ignored. For each treatment received, the worst severity observed for the subject within the observation period and AE class will be reported. The denominators for percent values will be indicated within the table or table header and denominators will consist of the maximal size of the safety population in the indicated observation period.

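### An adverse event still open at the next dose is counted only under the earlier treatment but graded at its worst later severity, so worsening after one treatment can be tabulated under another

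*SAP*

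**What the plan says.** SAP section 9 has a two-part rule for an AE whose dates overlap more than one period.

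- Attribution: "the AE will be associated with treatment immediately preceding the AE start date only".
- Severity: "the AE will be graded according to the maximum severity of the event at any time prior to the AE end date".

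SAP 3.3 gives the same attribution in general terms: "Treatment associated with post-dose records will always be the last type of treatment received before the (start) date or date-time associated with the record".

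SAP 9.3 describes the tabulated severity differently: "For each treatment received, the worst severity observed for the subject within the observation period and AE class will be reported". Neither section defines the observation period.

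Protocol 7.3, under eligibility for continued dosing, lets an AE be open at the next dose. One qualifying condition is "Any new or prior AEs were grade 1 or resolved"; another is "Any new or prior AEs that were grade 2, should be either resolved or downgraded to Grade 1". A Grade 3 AE judged unrelated may also have come down to Grade 1. Each condition also requires an investigator judgment about risk and confounding, and dosing may be delayed by up to 14 days. The same section sets a limit: "If a subject has a Grade 3 AE judged related to study drug administration, this subject will be withdrawn from the study".

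**The concern.** Attribution stops at the first treatment, while severity keeps running through later doses. If an AE begins mild after one treatment and becomes severe only after the next, the severe grade appears in the first treatment's column and the second treatment's column is empty. The by-treatment AE tables and figures serve the secondary objective on safety and tolerability of 2 g and 4 g zoliflodacin. In a crossover, their value depends on each event, and each grade, standing under the treatment that preceded it.

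**Working it through.** No figure in the plan can be reproduced here; this is a classification rule. The check has four steps.

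**1. Follow one case through the rule.** Take sequence CBDA (placebo, 4 g, moxifloxacin, 2 g) with doses on Days 1, 9, 17 and 25 (Protocol 7.4.2). A Grade 1 headache starts on Day 7, is still open at the 4 g dose on Day 9, and reaches Grade 3 that afternoon. The start date falls after placebo, so placebo is the only treatment assigned. The maximum grade before the end date is 3. The result is one severe headache under placebo and none under 4 g. A rise to Grade 2 would be misplaced in the same way, as a moderate event.

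**2. Look for a provision that prevents it.** It would not arise if the site opened a new AE record at the worsening.

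- Protocol 8.1.5 has worsening of existing conditions reported as AEs, but within the physical examination section, and it does not say that an open AE is closed and re-entered.
- Protocol 9.2.1 covers worsening of conditions present at screening, and 8.1.4 worsening of pre-dosing medical history.
- Protocol 9.2.1.2 names onset, severity, relationship and resolution among the items collected. It names no grade-change date.

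None of these clearly requires a new record for an AE that began on study.

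**3. Compare the other severity displays.**

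| Display | Severity window |
|---|---|
| AE spanning periods (SAP 9) | up to the AE end date, across later doses |
| AE incidence (SAP 9.3) | observation period, undefined |
| By-treatment AE figures (Figures 4–7, 9–12) | titles end the window at the next dose |
| Laboratory and vital-sign grading (SAP 9.6, 9.7) | within the period |
| Standard ECG grading (Table 28 footnote) | within the period |

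Only the SAP 9 rule for AEs runs across doses. A placebo figure built on it could show a grade reached only after zoliflodacin, against its own title.

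**4. Count directions and size.** Each ordered pair of treatments occurs side by side in 3 of the 12 listed sequences, with 6 subjects per sequence.

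- Placebo directly before zoliflodacin (CA, CB): 3 + 3 = 6 sequences, 6 × 6 = 36 subjects.
- Zoliflodacin directly before placebo (AC, BC): 3 + 3 = 6 sequences, 36 subjects.
- Moxifloxacin directly before zoliflodacin (DA, DB): 36 subjects. The reverse (AD, BD): 36 subjects.

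If all 72 subjects receive each treatment, one event is 1/72 = 1.4%; with 56 subjects it is 1/56 = 1.8%. In a severity row, the earlier column can be too high by that amount and the later column too low. In an any-severity row, the earlier column is already right because the AE did start there, and only the later one is short. With the Wilson intervals planned for Table 13, the later treatment's row would read 0/72 (0% to 5.1%) rather than 1/72 (0.3% to 7.5%), if that subject had no other AE in the category.

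**The case against.** The strongest reply is that start-date attribution at worst grade is an explicit, prespecified convention and that the case is rare. Doses are about 8 days apart and the stated zoliflodacin half-life is about 6 h, so 8 × 24 / 6 = 32 half-lives pass between doses. An AE must still be open, be at Grade 1, pass the investigator's judgment and then worsen. That stands as to frequency. It does not make the resulting grade right for the treatment it is printed under.

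A reader might draw four stronger conclusions that the documents do not support.

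- *The rule favours zoliflodacin or hides its signal.* It also loads worsening after placebo or moxifloxacin onto zoliflodacin, and the counts of adjacent pairs are equal. A related Grade 3 AE after zoliflodacin leads to withdrawal, which would appear in Listing 1 and in the tolerability summary (Table 32). Table 16 lists non-serious moderate or severe AEs with period, days post treatment and duration, so an event crossing a dose can be seen.
- *SAP 9 and 9.3 cannot both be programmed.* They can be applied in turn: section 9 fixes the treatment and grade of each record, then 9.3 takes the worst record per subject, treatment and class. What remains is that an undefined observation period does not settle where severity stops.
- *All later doses measure the size.* There are 72 × 3 = 216 of 72 × 4 = 288 planned dosings after the first, but these are opportunities, not expected events.
- *The timing can never be recovered.* Protocol 9.2.1.2 says what the AE information includes, which need not be the full list. The eCRF and the Manual of Procedures are not among the documents, and Table 15 does record when an event became serious. All that can be said is that no section provides grade-change dates for AEs in general.

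**Conclusion.** The point holds as a limited defect in the by-treatment AE reporting. Followed as written, SAP 9 can place a grade under a treatment given before that grade occurred, and leave the treatment that did precede it with no event. The direction is not fixed. The effect is 1.4 percentage points per misplaced event in an affected column, assuming 72 subjects per treatment and no other AE of the same class and grade in that subject under that treatment. The number of such events cannot be estimated from the documents and should be small.

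The displays at risk are Tables 12–14 for all AEs, and Figures 4–7 and 9–12 for related AEs; the listings in Tables 15 and 16 and Listing 8 carry the same treatment and grade. Laboratory, vital-sign and standard ECG grading and the primary QTcF analysis are unaffected. The conclusion assumes that the site keeps one record for an AE that worsens; if site practice already opens a new record, the problem does not arise, but neither document clearly requires it.

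**What to change.** 1. In SAP 9, limit the severity of an AE under a treatment to its worst grade before the next dose. Use the next dose as the boundary, because the periods in SAP 3.3 end the day before check-in.
2. In SAP 9.3, define the observation period the same way, so that text, tables and figure titles agree.
3. In Protocol 9.2.1.2, add that an ongoing AE whose grade rises after a later dose is recorded as a new, linked AE with its own onset, grade and relatedness, assigned to the later treatment.

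The first change depends on the third, or on grade-change dates in the eCRF; without one of these the severity cannot be cut at the dose. The cost is two short SAP edits and one recording instruction, which is a protocol change. A few continuing events will appear as two linked records, so a footnote should say so. The re-dosing criteria need no change for this purpose.
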